STUDY PROTOCOL
Social Behavioral Template

**Role Of Non-Specific Effects in The
Treatment of depression with Esketamine
(ROSETTE)**

Protocol Number

2000034829

Protocol Version

Version Date: 3/6/24

Version # 2

Clinical Trials Registration Number (if applicable)

NCT05910775

Confidentiality Statement:

Synopsis

Purpose

We aim to examine the magnitude of non-specific effects in the treatment of depressive episodes with esketamine, by providing patients in the “intervention” group with a pre-treatment presentation and post-treatment “follow up” session, to assess whether non-specific effects can be used effectively to improve the effectiveness of treatment with esketamine.

Objectives

Primary Objective:

To determine whether a positive presentation before first treatment improves expectation of improvement from treatment in patients receiving esketamine for a depressive episode within 24 hours after the first treatment.

Secondary Objectives:

To determine whether a post-treatment follow up session to provide encouragement and reassurance improves expectation of improvement from treatment in patients receiving esketamine for a depressive episode within 24 hours after the first treatment.

To determine whether a positive presentation results in an improved response from treatment in patients receiving esketamine for a depressive episode as measured by MADRS score within 24 hours after the first treatment.

To determine whether a positive presentation before first treatment, combined with a post-treatment follow up session after first treatment, result in an improved response from treatment in patients receiving esketamine for a depressive episode as measured by MADRS score by the end of the acute course of esketamine treatment.,

Study Population

Adult patients with major depressive disorder for whom it has been determined by their primary mental health provider that esketamine is an appropriate treatment and have already been deemed appropriate and scheduled for clinical esketamine treatment at Yale Interventional Psychiatry Service.

Number of Participants

We aim to enroll a total of 34 patients (17 per arm) for this study.

Study Design

Patients who are deemed clinically appropriate for esketamine will be approached for participation in the study. The eligible and consented participants will be randomized at a 1:1 ratio into “intervention” and TAU groups, with the intervention group being presented with the presentation prior to the first treatment, and to receive a “follow up” session within 24 hours after the first treatment. Both groups will otherwise receive treatment as usual during the course. Assessments including treatment expectations and depression severity will be done at baseline, within 24 hours after treatments 1, 2 and 8.

Study Duration

2 years

Outcome Variables

Primary outcome: Group difference in change in question 6 of the CEQ-6 from baseline to after the presentation

Secondary Outcome: Group difference in change in MADRS score from baseline to 24 hours after first treatment

Exploratory outcomes:

Group difference in change in CEQ-6 from baseline to 24 hours after first treatment and after follow-up session

Group difference in change in MADRS score by the end of the acute series of treatments

Group difference in the side effect profile

Locations/Facilities

Yale Psychiatry hospital (YPH) Interventional Psychiatry Services (IPS) unit

Abbreviations

Abbreviation	Explanation
AE	Adverse Events
CMP	Clinical monitoring plan
CEQ-6	Credibility and Expectancy Scale
CRF	Case report form
DCC	Data coordination center
DHHS	Department of Health and Human Services
DSMB	Data Safety Monitoring Board
DRE	Department of Health and Human Services
EC	Ethics Committee
eCRF	Electronic Case Report Forms
GCP	Good clinical practice
HIPAA	Health Insurance Portability and Accountability Act
MADRS	Montgomery-Asberg Depression Rating Scale
NCT	National Clinical Trial
NIH	National Institutes of Health
PI	Principal Investigator

QA	Quality Assurance
QC	Quality Control
QIDS-SR	Quick Inventory of Depressive Symptomatology
SAE	Serious Adverse Event
SAP	Statistical Analysis Plan
SMC	Safety Monitoring Committee
SOP	Standard Operating Procedure
TAU	Treatment as usual
UP	Unanticipated Problem
YCCI	Yale center for clinical investigation

Glossary of Terms

Glossary	Explanation
Adverse Event	Any event associated with esketamine treatment or the virtual presentation and follow-up sessions whether or not considered therapy related.
Dysgeusia	Altered taste

1.1 Background

Non-specific treatment effects and more specifically placebo effects have been recognized as major factors contributing to the effectiveness of various therapies for more than two centuries¹ As early as 1955 Beecher noted that placebo effects can be quite beneficial and should be studied further². However, more recently placebo effects have largely been viewed as a nuisance in the conduct of clinical trials and most efforts have been directed at minimizing the effect to better isolate the true specific-treatment effect³. Understanding the factors that contribute to the non-specific effects of a treatment, including the placebo and nocebo effects (negative effects experienced in concordance with the expected side effect) could improve our ability to provide effective treatment to patients with little added costs to the health care system⁴.

Significant advances have been made in our understanding of the basic factors contributing to the placebo and nocebo effects over last few decades⁵. It is theorized that the culmination of verbal, social and conditioned “cues” create an expectancy for a specific therapeutic response driving the powerful placebo effect⁵. Recent work has begun to elucidate the neurobiological mechanisms underlying this effect. While moderate to large placebo response rates have been observed in a broad range of medical diseases ranging from neurological disorders⁶ and depression^{7,8} to cardiovascular disorders⁹, much of the mechanistic research in this area has been focused on the study of pain management as it is most amenable to studies examining the rapid onset of the effect. The narrow scope of the mechanistic research leaves questions about generalizability and applicability of the findings to other disorders in question. The discovery of rapidly acting antidepressant medications such as ketamine now allows for the efficient investigation of placebo and nocebo effects in patients suffering from depression.

Yale has been a leader in the development of rapidly acting antidepressant treatments and the Interventional Psychiatry Service (IPS) at Yale Psychiatric Hospital (YPH) currently provides over 70 ketamine/esketamine treatments for major depressive disorder (MDD) per week. Throughout the conduct of nearly 20 years of clinical trials and 8 years of clinical care with these treatments, clinicians and investigators working in the program have been increasingly intrigued by the non-specific contributions of the treatments to the clinical response. The data from the existing phase 2 and 3 trials of esketamine¹⁰ have demonstrated much higher than expected rates of response in the placebo treated groups which also suggests a notable non-specific component to the treatment.

1.2 Prior Experience

NA.

2 Rationale/Significance

2.1 Rationale and Study Significance

Based on the available evidence, non-specific effects are thought to be responsible for a notable portion of treatments' effects and side effects. Considering the prevalence of depressive disorders and their significant burden on the society¹¹, any potential improvements in effectiveness can have far reaching benefits for our patients and the society. This project aims to methodologically examine the magnitude of non-specific effects in the treatment of depressive episodes with esketamine, to explore the moderators and mediators of the effect, and to assess whether the non-specific effects can be used effectively to improve the effectiveness of this treatment.

The data collected in this initial study will be used to provide support for future study proposals designed to more thoroughly evaluate the moderators and mediators of the effect employing the wide range assessment tools and imaging modalities available here at Yale. Furthermore, the laboratory model created through this initial study can be further optimized and modified for use with novel treatments currently under investigation for mental health and other disorders, namely psychedelic treatments.

2.2 Risks

Intervention-specific Risks

The main risk to participants in the current study consists of a change in the level of effectiveness and side effects from treatment as a result of the study intervention. Specifically, the “intervention” group may experience a different rate of response, or notice side effects to a different degree than the “treatment as usual” group.

Although non-specific effects in general are believed to be responsible for a significant portion of the treatment’s effects, as the current study only targets a small subcategory of non-specific factors, the magnitude of increased risk will be limited. Furthermore, the study is designed to create a difference between groups mainly by potentially improving the outcomes of the “intervention” group.

The “intervention” group may also experience more dysgeusia which is one of the mild and temporary side effects of esketamine, as a result of intentionally highlighting it in the presentation.

Additionally, the “intervention” group may experience some distress during the “post-treatment” session, particularly if they need to review and discuss distressing or uncomfortable experiences from the treatment.

Psychiatric Assessment and Symptom Rating

Discussing symptoms or past experiences can sometimes be stressful. All included evaluations are non-invasive and have been used without difficulty or adverse events in previous studies and clinical practice.

In order to minimize risks associated with the psychiatric ratings and ensure the accuracy of reporting, these measures will be administered by trained research staff. Participants will be informed that they do not need to answer any question on the rating scales or questionnaires that make them feel uncomfortable. Participants will also be informed they can take a break if they become tired from any of the questions or ratings.

Confidentiality

Loss of confidentiality is another potential hazard of any research protocol. The investigators follow a system of specific precautions to ensure the confidentiality of data in this protocol.

Private identifiable information will be collected (name, date of birth, age, telephone number, address, medical and psychiatric history, diagnoses, laboratory tests, and psychiatric rating scores) but will be kept confidential and will not be divulged in any publication emanating from this work. Please see section 8.1, for the protections in place to mitigate confidentiality risks.

2.3 Anticipated Benefits

Participants may or may not benefit from the study through improvement in their clinical outcomes. Both groups will have extensive contact with the research team in addition to the usual clinical care team, which may provide some additional benefit to patients. Participants will be paid for their participation in the study. They will be paid \$50 for completing each non-presentation visit (Screening visit, 24 hours post 1-st treatment, 72 hours post 8th treatment), which makes it up to 150 dollars in total if they complete the study. They will not be paid for the presentation visit. They will receive a debit card upon consenting and completing the screening visit and the reimbursement will be loaded to the card after completing each of the mentioned visits.

The results of this initial study would benefit the field by providing a better understanding of the role of non-specific effects, and whether and to what extent these effects can be optimized.

3 Study Purpose and Objectives

3.1 Purpose

We aim to examine the magnitude of non-specific effects in the treatment of depressive episodes with esketamine, by providing patients in the “intervention” group with a pre-treatment presentation and post-treatment “follow up” session, to assess whether non-specific effects can be used effectively to improve the effectiveness of treatment with esketamine.

3.2 Hypothesis

Hypothesis 1: A positive presentation highlighting the rapid onset effects and positive therapeutic outcomes observed in prior clinical trials and clinical care will increase the expectation of improvement from esketamine treatment compared to the treatment-as usual (TAU) group.

Hypothesis 2: A post-treatment “debriefing” session after first the treatment to provide encouragement and reassurance, will further consolidate the expectation of improvement from esketamine treatment.

Hypothesis 3: A positive presentation highlighting the rapid onset effects and positive therapeutic outcomes observed in prior clinical trials and clinical care combined with a post-treatment “debriefing” session after first the treatment to provide encouragement and reassurance will enhance treatment response compared to the TAU group.

Hypothesis 4: Highlighting a specific side effect during the presentation will result in a difference on the side effect profile of the treatment.

3.3 Objectives

Primary Objective:

To determine whether a positive presentation before first treatment improves expectation of improvement from treatment in patients receiving esketamine for a depressive episode within 24 hours after the first treatment.

Secondary Objective:

To determine whether a post-treatment debriefing session to provide encouragement and reassurance improves expectation of improvement from treatment in patients receiving esketamine for a depressive episode within 24 hours after the first treatment.

To determine whether a positive presentation result in an improved response from treatment in patients receiving esketamine for a depressive episode as measured by MADRS score within 24 hours after the first treatment.

To determine whether a positive presentation before first treatment, combined with a post-treatment debriefing session after first treatment, result in an improved response from treatment in patients receiving esketamine for a depressive episode as measured by MADRS score by the end of the acute course of esketamine treatment.

4 Study Design

Approach and consent:

Patients who are deemed clinically appropriate for esketamine will be approached for participation in the study. They will be provided with information regarding the study, including that they will be randomized into two groups with the “intervention” group receiving an informative presentation prior to the first treatment. They will be informed that the goal is to assess the effect of this presentation with regard to its ability to provide sufficient and appropriate information surrounding the treatment. Participants will not be informed at the time of recruitment that we hypothesize the content to potentially affect the tolerability and effectiveness of the treatment course. They will be informed about the full nature of the study

at a end of treatment debriefing session at the end of their participation (further details below).

Randomization

Participants will be randomized at a 1:1 ratio into “intervention” and TAU groups, with the intervention group being presented with the presentation prior to the first treatment, and to receive a “debriefing” session within 24 hours after the first treatment. Both groups will otherwise receive treatment as usual during the course.

Intervention

The intervention consists of a short presentation provided to the participants within 72 hours prior to the first treatment of the acute course (see study course below). Both groups will receive the information considered necessary for informed consent for esketamine treatment as part of usual clinical care. The presentation will be in addition to this process. The presentation will be factual, however it will emphasize the effectiveness of the treatment, and provide notable encouragement and reassurance. The actual treatments will be provided as usual with no change or alteration in dosing, course or other aspects of the treatment.

The intervention group will additionally receive a follow up session within 24 hours after the first treatment to provide encouragement and reassurance. There are two different versions for the follow up session, with each participant receiving one of the versions depending on whether they have noticed any improvements since the first treatment. The contents of these sessions will remain factual, but with differing emphasis on encouragement and reassurance depending on participants’ experience with the first treatment.

Study course

Participants in the intervention group will receive the presentation within 48 hours before the first treatment of the acute course of esketamine. They will also receive the follow up session within 24 hours after the first treatment, immediately after assessments are completed.

Assessments will be done at baseline, within 24 hours after treatments 1, 2 and 8, as detailed in Table 1. Assessments will be identical for both groups, with the exceptions described below.

Assessments

Intervention group specific assessments:

Participants will provide feedback regarding the presentation using a custom form (Appendix 1) before treatment 1 and at the end of treatment visit.

Assessments received by both groups:

Participants’ expectations will be assessed by Treatment Credibility and Expectancy Scale (CEQ-6).

[figure not shown]
Symptom severity will be assessed by a blinded assessor using a Clinician Rated Outcome questionnaire (MADRS) and a Patient Rated Outcome questionnaire (QIDS-SR16).

[figure not shown]
Side effects will be assessed by a custom questionnaire (Appendix 2) based on the side effects reported on the prescription label for esketamine.

End of treatment debriefing session:

A debriefing session will be held at the end of the study at the 1-month follow up visit, immediately after the last set of assessments are completed. During this session participants will be informed about the nature of the study in detail, including the hypothesized effects of non-specific factors on overall treatment efficacy, and [for participants in intervention group] the intentional emphasis of a minor side effect (dysgeusia) during the presentation compared to usual care. Participants will be given a chance to ask any questions regarding the study.

Study Flow Diagram

Prescreen

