4.2 Outcome Variables/Endpoints

4.2.1 Primary Outcome Variables/Endpoints

Primary outcome: Group difference in change in question 6 of the CEQ-6 from baseline to after the presentation

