4.2.2 Secondary and Exploratory Outcome Variables/Endpoints

Secondary Outcome: Group difference in change in MADRS score from baseline to 24 hours after first treatment

Exploratory outcomes:

Group difference in change in CEQ-6 from baseline to 24 hours after first treatment and after follow-up session

Group difference in change in MADRS score by the end of the acute series of treatments

Group difference in the side effect profile

5 Study Participants

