6.1 Study Procedures

Potential subjects will be referred to the study team by the interventional psychiatry physician who has seen the patient in clinical evaluation for esketamine, after ascertaining their agreement to be approached for the study. At this time, the patient will be reached out by a study team member and informed about the study.

Screening / Intake Visit

It is estimated the screening intake will take approximately 2 hours. It will consist of the following procedures and assessments and can be completed in up to 5 days:

- a. Informed Consent: A delegated study team member will discuss risks and benefits of participation and review the study overview with the patient as explained above. The patient will sign the informed consent form prior to any study procedures being performed.
- b. Clinical and Demographic Intake (including medical and psychiatric history, medication history, and current medications)
- c. Montgomery-Asberg Depression Rating Scale (MADRS) and Quick Inventory of Depressive Symptomatology (QIDS-SR16)
- d. CEQ-6 questionnaire regarding upcoming treatment course with esketamine
- e. Review of Inclusion/Exclusion Criteria by investigator

Presentation Visit (Intervention group only)

The intervention consists of a short virtual (via Zoom or similar technology) presentation provided to the participants, within 72 hours before the first treatment with esketamine. The presentation includes predetermined slides and content (the presenter will cover the same

slides and topics but will avoid a strict script to retain the personalized feeling of the presentation, an aspect believed to be crucial to the non-specific effects. Further, patients are allowed to engage, ask questions etc.) The presentation will remain factual and provide information from peer-reviewed literature. However, it is designed to convey a strong positive message, highlighting the effectiveness of the treatment. Additionally, a mild and temporary known side effect of the treatment (dysgeusia) will be intentionally highlighted to assess the 4th hypothesis.

Treatment visits:

Both groups will receive the usual treatment and care. Immediately before first and second treatments both groups will complete the CEQ-6 questionnaire. Additionally, the intervention group will complete the presentation feedback form prior to the first treatment. The rest of the treatments (i.e. treatments 3 to 8) will be done without any assessments.

Follow-up visit:

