7.2 Planned Analyses

Data will be examined prior to analysis using descriptive statistics, presented as means \pm SD or median (interquartile range) for continuous characteristics, and as frequencies (%) for categorical characteristics.

Where appropriate, randomized groups will be compared on baseline continuous characteristics (e.g. age) using two-sample Welch's t-test or Wilcoxon rank sum test, and on categorical characteristics using the chi-square test or Fisher's exact test as appropriate. Continuous outcome measures will be assessed for normality using histograms and Q-Q plots, and transformations will be applied as necessary. Between groups primary and secondary outcomes (CEQ-6, MADRS and QIDS) will be considered significant using a two-tailed alpha threshold of 0.05.

The primary and secondary outcomes (CEQ-6, MADRS, QIDS) will be compared between groups using a linear mixed model with group (intervention, TAU) included as a between-subjects factor and time (see study timepoints) included as a within-subjects factor. The group by time interaction will be modeled. The correlation between multiple measurements in different timepoints within each subject will be modeled with random effects with the best-fitting model determined using information criteria.

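### The declared primary outcome, change in CEQ-6 question 6 up to the first treatment, is matched neither by the time in the primary objective nor by the test in section 7.2

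*Combined protocol and SAP*

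**What the plan says.** **Objective.** In the Synopsis and section 3.3, the primary objective is to find out whether a positive presentation "improves expectation of improvement from treatment in patients receiving esketamine for a depressive episode within 24 hours after the first treatment". It names no instrument or item.

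**Outcome.** The Synopsis and section 4.2.1 both give the primary outcome as "Group difference in change in question 6 of the CEQ-6 from baseline to after the presentation". Section 4.2.2 puts the later change among the exploratory outcomes: "Group difference in change in CEQ-6 from baseline to 24 hours after first treatment and after follow-up session".

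**Schedule.** Section 6.1 places the presentation "within 72 hours before the first treatment with esketamine", for the intervention group only. It then says: "Immediately before first and second treatments both groups will complete the CEQ-6 questionnaire". Table 1 marks expectations at four times: screening, immediately before Treatment 1, 24 hours after dose 1, and immediately before Treatment 2. The summary sentence in section 4 (Study course) reads "Assessments will be done at baseline, within 24 hours after treatments 1, 2 and 8, as detailed in Table 1". That sentence and its counterpart in the Synopsis leave out the pre-Treatment 1 reading.

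**Analysis.** Section 7.2 states: "The primary and secondary outcomes (CEQ-6, MADRS, QIDS) will be compared between groups using a linear mixed model". Group is the between-subjects factor, time (all study timepoints) is the within-subjects factor, and their interaction is modelled. The section mentions neither question 6 nor a primary contrast. Section 7.3 restates the primary question without a time or an item.

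**The concern.** Objective, outcome and analysis should point to the same quantity, and here they do not. The objective's time is that of an exploratory outcome. The outcome's time falls before any drug is given. The analysis fixes neither the item nor the time.

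The two times measure different things. Immediately before Treatment 1, the presentation is the only part of the intervention that has been delivered. Twenty-four hours after the first dose, the patient has had esketamine and may or may not have noticed a benefit; the protocol itself chooses the follow-up content on that basis. If the two readings disagree, the declared outcome could fail while the objective as worded is met, or the reverse. Separately, a significant interaction from the model in 7.2 would not show that expectation had changed at the declared time.

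**Working it through.** **1. Which reading is the declared outcome?** The presentation comes at most 72 hours before Treatment 1. The only CEQ-6 between it and the first dose is the one immediately before Treatment 1, which both groups complete. The outcome text does not name that visit, but no other reading fits, because the 24-hour change is listed separately.

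**2. The chain side by side.**

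| Place | Measure | Time |
|---|---|---|
| Primary objective (Synopsis, 3.3) | Expectation, no item | Within 24 h after Treatment 1 |
| Primary outcome (Synopsis, 4.2.1) | CEQ-6 question 6 | After the presentation, so before Treatment 1 |
| Exploratory outcome (Synopsis, 4.2.2) | CEQ-6 | 24 h after Treatment 1, and after the follow-up session |
| Analysis (7.2) | CEQ-6, no item | All study timepoints |
| Restated question (7.3) | Expectation, no item | None |

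The objective's time agrees with the third row, not the second.

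**3. What the model in 7.2 tests.** With 2 groups and 4 CEQ-6 times, and time categorical, the interaction has (2 − 1) × (4 − 1) = 3 degrees of freedom. The declared outcome is one contrast, with 1 degree of freedom. If time were entered as a linear trend, the interaction would have 1 degree of freedom, but it would be a difference in slopes and still not that contrast.

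**4. Why the difference matters (illustration).** Assumptions: 17 per arm, equal correlation among the four readings, known variance, and a group difference of d at one post-baseline time only, in SDs of change.

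- Take the d that the 1-df contrast detects with 80% power at two-sided 0.05: d = √(2/17) × (1.960 + 0.842) = 0.961.
- The 3-df test then has noncentrality 0.75 × n × d² = 0.75 × 17 × 0.961² ≈ 11.77. Against the critical value of 7.81, the chance of significance is about 83%.
- By symmetry the noncentrality is the same whether the difference lies before Treatment 1, at 24 hours, or before Treatment 2.

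So the interaction would be significant about 83% of the time even if the difference existed only at 24 hours and was zero at the declared time. The problem is not lost power (83% against 80% here) but that the test does not locate the effect.

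**5. Choosing between the two times (illustration).** If either time could be reported as primary at two-sided 0.05, with no true effect:

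- independent statistics: 1 − 0.95² = 9.75%;
- correlation 0.3, 0.5, 0.7 or 0.9 (bivariate normal): about 9.5%, 9.1%, 8.3% or 7.0%.

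The documents give no correlation. The range is therefore an assumption, and the calculation presumes a choice that the outcome list does not offer.

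**The case against.** The best reply is that the primary endpoint is already fixed. The Synopsis and section 4.2.1 use identical words, with one item and one change window, and the schedule identifies the visit. That stands: a reader might infer that the trial has no single primary time or measure, and the outcome sections do not support that.

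Four further points limit the concern.

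- A reader might infer that the TAU arm has no comparable reading because it gets no presentation. It does have one: section 6.1 and Table 1 give both groups the CEQ-6 immediately before Treatment 1. Only the label is loose.
- A reader might infer that the plan permits reporting whichever time and measure succeeds. It does not: the 24-hour change is expressly exploratory.
- A reader might take 7.2 to make the whole scale a second primary measure. The text mentions no total and can be read as a list of instruments. The gap is under-specification.
- The 24-hour comparison is not invalid. Both arms receive esketamine, and the follow-up session comes after the 24-hour assessments. The difference is still a randomized comparison of the presentation's effect, including any part that acts through early response. It is a different estimand.

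None of this removes the mismatch. The objective still asks about a time that the outcome list calls exploratory, and 7.2 still does not state the test of the declared outcome.

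**Conclusion.** The concern holds as a misalignment. The declared primary outcome is recoverable as the change in question 6 from screening to immediately before Treatment 1, but the primary objective names another time, and the analysis names neither the item nor the contrast. This bears on the trial's main result and should be settled before the data are analysed, since a later choice could look data-driven.

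The textual finding rests on no assumed number. Placing the declared reading immediately before Treatment 1 is an inference from section 6.1 and Table 1. The 3 degrees of freedom assume categorical time, and the 83% assumes equal correlation and known variance. The 7% to 10% range rests on assumed correlations and on a free choice between times. It illustrates the exposure and is not an estimate of this trial's error rate.

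**What to change.** - **Synopsis and 3.3:** align the time in the primary objective with the declared outcome, that is, immediately before the first treatment.
- **Synopsis and 4.2.1:** name the visit for both arms as the CEQ-6 completed immediately before Treatment 1.
- **7.2:** state that the primary test is the between-group contrast in change in question 6 from screening to that visit, estimated from the mixed model at two-sided 0.05. Say that the 24-hour reading and the other CEQ-6 items remain exploratory.
- **Synopsis (Study Design) and section 4 (Study course):** correct the sentence on assessment times so that it includes the pre-Treatment 1 CEQ-6 and agrees with Table 1.

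The cost is a wording amendment, which section 9.1 requires the IRB to approve before use. It keeps the endpoint already declared and needs no new visits, data or patients.
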